7.3. Participant Discontinuation/Withdrawal From the Study

All efforts should be made to ensure participants are willing to comply with study participation prior to conducting the screening procedures. The study staff should notify Alexion and their site monitor of all study withdrawals as soon as possible. The reason for participant discontinuation must be recorded in the source documents and eCRF.

A participant may withdraw from the study at any time at his/her own request, or may be withdrawn at any time at the discretion of the Investigator for safety, behavioral, compliance, or administrative reasons. This is expected to be uncommon.

At the time of discontinuing from the study, if possible, an early discontinuation visit should be conducted, as shown in the SoA. See SoA (Section 1.3) for data to be collected at the time of study discontinuation and follow-up and for any further evaluations that need to be completed.

The participant will be permanently discontinued both from the study intervention and from the study at that time.

If the participant withdraws consent for disclosure of future information, Alexion may retain and continue to use any data collected before such a withdrawal of consent.

If a participant withdraws from the study, he/she may request destruction of any samples taken and not tested, and the Investigator must document this in the site study records.

In order to meet minimum data requirements for SRC meetings, participants who withdraw consent from the study within the first 14 days may be replaced. At the Sponsor's discretion, and after consultation with the SRC, up to 18 additional participants may be enrolled as replacement participants if a participant discontinues prior to Day 43 for reasons other than drug-related AEs.

7.4. Lost to Follow-up

A participant will be considered lost to follow-up if he or she repeatedly fails to return for scheduled visits and is unable to be contacted by the study site.

The following actions must be taken if a participant fails to return to the clinic for a required study visit:

- The site must attempt to contact the participant and reschedule the missed visit as soon as possible and counsel the participant on the importance of maintaining the assigned visit schedule and ascertain whether or not the participant wishes to and/or should continue in the study.
- Before a participant is deemed lost to follow-up, the Investigator or designee must make every effort to regain contact with the participant (where possible, email, 3 telephone calls and, if necessary, a certified letter to the participant's last known mailing address or local equivalent methods). These contact attempts should be documented in the participant's medical record.
- Should the participant continue to be unreachable, he/she will be considered to have withdrawn from the study.

Discontinuation of specific sites or of the study as a whole are handled as part of Section 10.1.8.

8. STUDY ASSESSMENTS AND PROCEDURES

Study procedures and their timing are summarized in the SoA (Section 1.3). Protocol waivers or exemptions are not allowed.

Immediate safety concerns should be discussed with Alexion immediately upon occurrence or awareness to determine if the participant should continue or discontinue study intervention.

Adherence to the study design requirements, including those specified in the SoA, is essential and required for study conduct.

All screening evaluations must be completed and reviewed to confirm that potential participants meet all eligibility criteria. The Investigator will maintain a screening log to record details of all participants screened and to confirm eligibility or record reasons for screening failure, as applicable.

Procedures conducted as part of the participant's routine clinical management (eg, blood count) and obtained before signing of the ICF may be utilized for screening or baseline purposes provided the procedures met the protocol-specified criteria and were performed within the time frame defined in the SoA, if consistent with site SOP.

8.1. Efficacy Assessments

No efficacy assessments will be obtained during this study.

8.2. Safety Assessments

Planned time points for all safety assessments are provided in the SoA (Section 1.3).

8.2.1. Physical Examination

A complete physical examination will include, at a minimum, assessments of the general appearance; skin; head, ears, eyes, nose, and throat; neck; lymph nodes; chest; heart; abdominal cavity; limbs; central nervous system; and musculoskeletal system. Weight will also be measured and recorded.

Height and BMI will be recorded at Screening only.

Investigators should pay special attention to clinical signs related to previous serious illnesses.

8.2.2. Vital Signs

Vital sign measurements will be taken after the participant has been resting in the supine or semi-recumbent position for at least 5 minutes and will include temperature (tympanic or oral), respiratory rate, supine blood pressure, and pulse. Orthostatic (standing) blood pressure will only be measured at Screening.

The timing of vital sign measurements is described in the SoA (Section 1.3).

Out of range blood pressure or pulse measurements will be repeated at the Investigator's discretion. Confirmed, clinically significant vital sign measurements will be recorded as AEs.

8.2.3. Electrocardiograms

Triplicate 12-lead ECGs will be recorded at the time points described in the SoA (Section 1.3) to obtain heart rate, PR, QRS, and QT intervals. 12-lead ECG recordings will be made after the participants have been resting in a supine position for at least 10 minutes.

At each time point at which triplicate ECGs are required, 3 individual ECG tracings should be obtained as closely as possible in succession but no more than 2 minutes apart.

8.2.3.1. Safety Review of 12-lead Electrocardiograms

All recorded ECGs will be reviewed by the Investigator or qualified designee. If a participant shows an abnormal ECG, additional safety recordings (including the use of 5- or 12-lead Holter equipment) may be made, and the abnormality will be followed to resolution.

8.2.3.2. 24-hour Holter Electrocardiograms/Real Time Display (Cardiac Telemetry)

Holter recording will be performed up to 3 months prior to Day 1, and telemetry will be used on dosing days as specified in Section 1.3. Electrocardiogram telemetry will be monitored by the Investigator or qualified member of clinical staff. This will allow the extraction of 10-second 12-lead ECG data files, which can be transferred onto the MUSE. All ECG files so acquired will then be analyzed and over-read using the same process as for any other 12-lead ECG. The ECG Holter/telemetry reports will be archived with study documents.

8.2.4. Clinical Laboratory Assessments

See Section 10.2 for the list of clinical laboratory tests to be performed and to the SoA (Section 1.3) for the timing and frequency. Clinical and laboratory assessments will be performed by a local laboratory to assess safety.

The Investigator must review the laboratory report, document this review, and record any clinically relevant changes occurring during the study in the AE section of the eCRF. The laboratory reports must be filed with the source documents. Clinically significant abnormal laboratory findings are those which are not associated with the underlying disease, unless judged by the Investigator to be more severe than expected for the participant's condition.

All laboratory tests with values considered clinically significantly abnormal during participation in the study should be repeated until the values return to normal or baseline or are no longer considered clinically significant by the Investigator or Medical Monitor.

- If such values do not return to normal/baseline within a period of time judged reasonable by the Investigator, the etiology should be identified, and Alexion notified.
- All protocol-required laboratory assessments, as defined in Section 10.2, must be conducted in accordance with the laboratory manual and the SoA.

If laboratory values from non-protocol specified laboratory assessments performed at the institution's local laboratory require a change in participant management or are considered clinically significant by the Investigator (eg, SAE or AE or dose modification), then the results must be recorded in the eCRF.

The maximum total blood volume collected from participants participating in this study will not exceed 500 mL every 16 weeks.

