6.3. Measures to Minimize Bias: Randomization and Blinding

This is a double-blind study. Eligible participants who meet all inclusion and no exclusion criteria will be assigned unique numbers for enrollment and randomization.

For all cohorts, dosing will be double-blinded to active versus placebo. Participants will be randomly assigned in a 3:1 ratio to active treatment or placebo.

During dosing, the participants and on site medical/nursing staff at the study center, and the Sponsor will be blinded to study drug assignment. The pharmacy staff preparing the SC/IV doses will not be blinded, nor will the study drug administrator(s), while all other study center staff involved in the safety evaluations will remain blinded to study drug assignment. Because the appearance of the placebo does not match that of the active study drug, a masking technique will be used at the time of administration (see pharmacy manual for details).

Sponsor staff will be unblinded only when necessary (eg, to monitor that the SC/IV dosing are being prepared appropriately, to determine reportability of SAEs, and evaluate PK/PD data for dose escalation decisions), and will refrain from sharing any information on study drug assignment with the study center staff or others at the Sponsor, especially with regard to assessment and reporting of safety. An unblinded study drug administrator will administer study drug; an appropriate unblinded physician or senior pharmacy staff member will review CAP activity results and make decisions regarding antibiotic treatment.

In the event of an emergency, an envelope for each participant containing his or her study drug assignment will be available from the pharmacy staff preparing the study drugs. There is no antidote to reverse the effects of ALXN1820; therefore, unblinding would not be helpful in the planning of participant treatment for a given event.

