Escalation to Cohort 7 (optional)	SRC	All available data up to a minimum of 336 hours post-dose safety and tolerability data from at least 7 participants (of whom at least 5 will have received treatment) from Cohort 6 and 672 hours post-dose PK/PD data for Cohorts 4 and 5 from at least 7 participants (of whom at least 5 will have received treatment) from each cohort. Cohort 7 may not be initiated based on SRC review.	The SRC will document the decision on the escalation/progression approval form.

Table 19: Study ALXN1820-HV-101 Dose Continuation/Escalation Decision Pathway

Dosing Decision	Responsible Party	Data to be Reviewed	Documentation/Communication Methods
Proceed to Cohort 8 and 9	SRC	All available data up to a minimum of 336 hours post-dose safety and tolerability data from at least 7 participants (of whom at least 5 will have received treatment) from Cohorts 4 and 5.	The SRC will document the decision on the escalation/progression approval form.
Escalation to Cohort 10	SRC	All available data up to a minimum of 672 hours post-dose safety and tolerability data from at least 7 participants (of whom at least 5 will have received treatment) from Cohort 8, and 672 hours post-dose PK/PD data for Cohorts 4 and 5 from at least 7 participants (of whom at least 5 will have received treatment) from each cohort.	The SRC will document the decision on the escalation/progression approval form.

Abbreviations: IV = intravenous; PD = pharmacodynamic(s); PK = pharmacokinetic(s); SRC = Safety Review Committee.

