8.5. Pharmacokinetics

Whole blood samples will be collected for measurement of serum concentrations of ALXN1820 as specified in the SoA (Section 1.3). Additional samples may be collected at additional time points during the study if warranted and agreed upon between the Investigator and Alexion. The total blood volume will not exceed the volume limit for healthy participants (Section 8.2.4). The timing of sampling may be altered during the course of the study, based on newly available data (eg, to obtain data closer to the time of peak plasma concentrations) to ensure appropriate monitoring.

- Instructions for the collection and handling of biological samples will be provided by Alexion. The actual date and time (24-hour clock time) of each sample will be recorded.
- Samples will be used to evaluate the PK of ALXN1820. Samples collected for analyses of ALXN1820 serum concentration may also be used to evaluate safety or efficacy aspects related to concerns arising during or after the study.
- Samples may be used for research to develop methods, assays, prognostics and/or companion diagnostics related to dysregulated complement activity.

Study intervention concentration information that may unblind the study will not be reported to investigative sites or blinded personnel until the study has been unblinded.

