10.2. Appendix 2: Clinical Laboratory Tests

- The tests detailed in [Table 23](#) will be performed by the local laboratory.
- Protocol-specific requirements for inclusion or exclusion of participants are detailed in [Section 5](#) of the protocol.
- Additional tests may be performed at any time during the study as determined necessary by the Investigator or required by local regulations.
- Pregnancy testing: Women of childbearing potential should only be enrolled after a negative serum pregnancy test result at Screening. Additional urine pregnancy testing will be standard for the protocol unless serum testing is required by site policies, local regulation, or IRB/IEC and should be performed per the time points specified in the SoA ([Section 1.3](#)).

Table 23: Protocol-Required Safety Laboratory Assessments

Laboratory Assessments	Parameters
Hematology	
 • Platelet count • Red blood cell (RBC) count • Hemoglobin • Hematocrit • RBC indices (MCV, MCH, %reticulocytes) • White blood cell (WBC) count with differential (neutrophils, lymphocytes, monocytes, eosinophils, basophils)
Clinical chemistry ^a	
 • Alanine aminotransferase (ALT)/serum glutamic-pyruvic transaminase (SGPT) • Alkaline phosphatase • Aspartate aminotransferase (AST)/serum glutamic-oxaloacetic transaminase (SGOT) • Blood urea nitrogen (optional) • Calcium • Creatinine • Creatine kinase • Hemoglobin A1C • Potassium • Sodium • Serum albumin • Total and direct bilirubin • Total protein • Urea
Coagulation	
 • Prothrombin time, partial thromboplastin time, international normalized ratio
Routine urinalysis	
 • Specific gravity • pH, glucose, protein, blood, ketones, bilirubin, urobilinogen, nitrite, leukocyte esterase by dipstick • Microscopic examination (if any leucocytes, more than a trace protein, nitrites, and blood [if not menstruating] are abnormal)
Complement activity	
 • Change in CAP activity using the Wieslab AP assay • Change in CCP and LP activities
Other screening tests	
 • Serum QuantiFERON®-TB test • Alcohol breath and urine drug screen (to include at minimum: amphetamines, barbiturates, benzodiazepines cocaine, opiates, phencyclidine, methamphetamine, 3,4

Table 23: Protocol-Required Safety Laboratory Assessments

Laboratory Assessments	Parameters

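### Table 23 and Section 8.2.4 place change in CAP activity in the laboratory reports the blinded Investigator must review, which conflicts with Section 6.3 and the Schedule of Activities

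*Protocol*

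**What the plan says.** **Text that sends CAP results to the Investigator.** Table 23 in Protocol Section 10.2 sets out the required safety laboratory assessments. Its complement activity row reads "Change in CAP activity using the Wieslab AP assay • Change in CCP and LP activities". The section states that the tabled tests "will be performed by the local laboratory". Section 8.2.4 ties itself to that list: "All protocol-required laboratory assessments, as defined in Section 10.2, must be conducted in accordance with the laboratory manual and the SoA". It also states: "The Investigator must review the laboratory report, document this review, and record any clinically relevant changes occurring during the study". Those changes go into the AE section of the eCRF, the reports are filed with the source documents, and values judged clinically significantly abnormal are to be repeated. No test in Table 23 is excepted.

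**Text that keeps CAP results from the Investigator.** Section 6.3 says that "an appropriate unblinded physician or senior pharmacy staff member will review CAP activity results and make decisions regarding antibiotic treatment". It keeps the staff who evaluate safety blinded and allows the Investigator unblinded information only where safety is judged to require it. Section 8.2.9 continues antibiotics for the whole cohort until every member has normalized, expressly to protect the blind.

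**Explicit withholding of results.** Section 8.5 says "Study intervention concentration information that may unblind the study will not be reported to investigative sites or blinded personnel" until the study is unblinded. Section 8.6, which covers properdin, CAP and CCP, has no such sentence.

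**The concern.** CAP activity is the drug's pharmacodynamic target. At most doses in this study a post-dose CAP value is close to a treatment label. The primary endpoint is safety, and Section 10.3.3 makes the Investigator judge causality for every AE. The individual and cohort stopping rules (Tables 20 and 21) count events related to ALXN1820. If the Investigator saw CAP results, relatedness judgements could be made with knowledge of assignment, and the stopping-rule counts that rest on them would be affected too. A site or local laboratory reading only Table 23 and Section 8.2.4 would find nothing telling it to hold these results back.

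**Working it through.** **1. Does Table 23 mean a post-dose result?**

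| Source | What it indicates |
|---|---|
| Table 23 wording, "Change in CAP activity using the Wieslab AP assay" | Post-dose: a change needs a later value as well as a baseline |
| Section 3, Table 13 | Post-dose: the secondary PD endpoint is worded the same way |
| Section 8.2.9 | Post-dose: the Wieslab AP assay is the one named for on-study CAP monitoring |
| Schedule of Activities, complement activity row and footnote | Screening only: an eligibility check by any suitable assay |
| Schedule of Activities, PD panel row | Post-dose CAP sits here, apart from the safety laboratory rows |
| SAP Section 11.2 | Complement activity is not among the safety laboratory parameters |
| SAP Section 10 | CAP, CCP and lectin pathway activity are PD measures |

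A post-dose result is therefore an inference from the wording of Table 23, though a natural one. The Schedule of Activities and the SAP point the other way, so Table 23 is the outlier.

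**2. Can the instructions all be followed?** On the post-dose reading, no. Sections 10.2 and 8.2.4 together put a CAP change in a report the Investigator must review and file. Section 6.3 gives that review to someone else and keeps the Investigator blinded.

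**3. How revealing would a CAP result be?** Predictions are from Table 16 (Table 22 agrees where it gives a figure). Complete CAP inhibition means more than 80% from baseline (Section 4.3). Days are counted from the first dose.

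| Cohort | Regimen | Complete CAP inhibition (days) | Maximum properdin inhibition (%) |
|---|---|---|---|
| 1 | 12.5 mg SC | 0 | 44 |
| 2 | 50 mg SC | 4 | 99.717 |
| 3 | 150 mg SC | 16 | 99.936 |
| 4 | 450 mg SC | 39 | 99.981 |
| 5 | 450 mg IV | 39 | 99.995 |
| 6 | 1200 mg SC | 67 | 99.993 |
| 7 (optional) | dose to be determined | none given | none given |
| 8 and 9 | 150 mg SC QW × 5 | 66 | 99.936 |
| 10 | dose to be determined, QW × 3 | 65 | 99.97 |

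Planned size: 10 cohorts × 8 = 80, which reproduces Section 9.2. Nine cohorts have a prediction: 9 × 8 = 72 participants. Eight of them (2 to 6, 8, 9 and 10) have complete CAP inhibition predicted: 8 × 8 = 64. Cohort 10 counts on the Table 16 figure, although its dose is not yet set. Without it the count is 56 of 64.

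**4. How many single-dose samples fall in that window?** After the end-of-infusion sample, Tables 4 and 5 schedule PD samples at 2, 4, 8 and 12 hours and at 1, 2, 4, 7, 14, 21, 28, 35, 42, 49, 56, 70, 84, 98 and 126 days after dosing, 19 in all. The number at or before the predicted duration is:

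- Cohort 1 (0 days): 0
- Cohort 2 (4 days): 7
- Cohort 3 (16 days): 9
- Cohorts 4 and 5 (39 days): 12 each
- Cohort 6 (67 days): 15

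These counts start the window at dosing. Samples taken before inhibition is complete would lower them.

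**The case against.** The best defence is that the specific blinding rules should prevail over generic laboratory text. Section 6.3 names an unblinded reviewer for exactly this result and restricts the Investigator to blinded information in general, which covers CAP and properdin whether or not Section 8.6 says so. Section 8.2.4 defers to the laboratory manual and the Schedule of Activities for how tests are run. The manual is not available and may already route these results correctly.

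Much of this stands. A reader might infer that the plan routinely discloses assignment to the Investigator. The documents do not support that: the stated process in Section 6.3 is the opposite, and disclosure follows only if Table 23 and Section 8.2.4 are taken literally. A reader might also infer that every participant's assignment is exposed. Cohort 1 has no predicted CAP inhibition and Cohort 7 has no prediction.

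A third tempting inference is that SRC review unblinds the Investigators, who are members (Section 9.5), because Table 19 includes Day 29 PK/PD data from Cohorts 4 and 5. No text says they receive participant-level values. Section 6.6 describes the reviewed data as blinded, Section 6.3 has Sponsor staff unblinded for that evaluation and bars them from sharing assignment with the site, and the SRC charter is not available.

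The defence does not remove the conflict. Section 6.3 allows unblinded information where safety requires it, and Table 23 labels CAP a safety test. The protocol saw a need to state the withholding rule for concentrations in Section 8.5, yet left it out of Section 8.6.

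**Conclusion.** The protocol contains an unreconciled conflict over who sees CAP results. It is a drafting defect with a possible consequence for the blind. It is not evidence that unblinding is planned or will occur. If the Table 23 route were followed, CAP results could reveal assignment in cohorts holding 64 of the 72 planned participants with a prediction, to the person whose causality judgements feed the primary safety endpoint and the stopping rules.

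This rests on four assumptions: that the Table 23 row refers to post-dose values; that the Table 16 predictions are roughly right; that CAP in placebo participants stays near baseline; and that the laboratory manual does not already withhold these results. The size comes from CAP, with properdin as support. The documents give no prediction for CCP or LP, and Section 4.3 reports no classical-pathway effect with the earlier properdin antibody ALXN1510. The SRC route remains an open question.

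**What to change.** - **Table 23:** restrict the complement activity row to the Screening test for complement deficiency, as in the Schedule of Activities, and remove the CAP, CCP and LP change items from the local safety list.
- **Section 8.6:** add the equivalent of the Section 8.5 restriction. Post-dose total and free properdin, CAP, CCP and LP results are not reported to blinded site staff and go only to the unblinded reviewer in Section 6.3 and the unblinded PK/PD analysts.
- **Section 8.2.4:** add a cross-reference to that restriction, so that the duty to review laboratory reports does not extend to these results.
- **Section 6.6 and Table 19 (secondary):** state that blinded SRC members see only model projections or non-identifying summaries of the Cohort 4 and 5 PK/PD data, unless the charter already says so.

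The cost is protocol wording and a routing instruction in the laboratory manual. No samples or visits are added, and the unblinded reviewer already exists.
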